Therapist attitudes toward evidence-based treatments. The *Evidence-Based Practice Attitudes Scale (EBPAS)*¹³⁸ assesses mental health provider attitudes toward evidence-based practices and adopting new interventions. Fifteen EBPAS items assess the extent to which the therapist: (a) would adopt a new practice if it made sense and was used by trusted colleagues (*Appeal* subscale); (b) would adopt a new practice if it was required by their agency (*Requirements* subscale), (c) is open to trying new treatments (*Openness* subscale), and (d) believes research-based interventions are not clinically useful (*Divergence* subscale). Respondents rate their agreement with items on a scale from 0 (*not at all*) to 4 (*to a great extent*), resulting in four subscale scores and an EBPAS Total Score reflecting overall positive disposition toward adopting evidence-based treatments and protocols. Therapists will complete the EBPAS prior to completing their training, and again after completing training.

Therapist openness to exposure therapy. The *Therapist Beliefs about Exposure Therapy Scale (TBES)*¹³⁹ is a therapist self-report questionnaire that measures negative attitudes they may hold about exposure therapy (e.g., "Compared to other psychotherapies, exposure therapy leads to higher dropout rates"). Respondents rate their agreement with each of 21 beliefs about exposure therapy along a 5-point scale (0=*disagree strongly*; 4=*agree strongly*). Items are summed, resulting in a TBES Total Score (range: 0-84), with higher scores reflecting more negative views of exposure therapy. Therapists will complete the TBES prior to completing their training and again after completing training.

Therapist knowledge about child anxiety and CBT. An 8-item *Knowledge Test* was created to assess therapists' familiarity with basic research findings about child anxiety (e.g., fear is a natural emotion; physical sensations of anxiety cannot harm a child; differences between fear and anxiety) and its evidence-based treatment (e.g., the three-component model of CBT; the value of exposures). Therapists will complete this knowledge test prior to completing their training and again after completing training.

Therapist self-efficacy. Therapists will complete the *Therapist Self-Efficacy Scale-CBT for Anxiety in Youth* (TSES-CAY),¹⁴⁰ a 16-item survey that measures the extent to which therapists perceive they are capable of competently conducting CBT for youth anxiety. Items from a therapist self-efficacy scale for the treatment of adult depression¹⁴¹ were adapted to assess therapist perceptions of their abilities treating anxiety in children and adolescents. TSES-CAY factor analysis has identified a three-factor structure: (a) *CBT/Anxiety-Specific Self-Efficacy* (which measures perceived ability to conceptualize client problems using the CBT model, maintain the structure of CBT, teach CBT skills, putting anxious patients in anxiety-provoking situations, and instruct patients to practice skills outside of session); (b) *Common Factors Self-Efficacy* (which measures perceived ability to build therapeutic alliance, empathize with children/families, etc); and (c) *Patient Responsivity Self-Efficacy* (which measures perceived ability to adapt to patient/family needs, work collaboratively with patients/families, and address treatment barriers as they arise). Therapists will complete all three scales of the TSES-CAY prior to completing their training. After completing their training, therapists will again complete the TSES-CAY CBT/Anxiety-Specific Self-Efficacy scale.

Organizational climate of treatment setting. The *Texas Christian Association Organizational Readiness for Change scale (TCU ORC)*¹⁴² will be used to assess organizational attributes and motivational factors of the clinical settings participating in the trial that can impact the overall success of treatment implementation. Prior to training and onboarding for the trial, therapists, supervisors, administrative directors, and staff across the clinics participating in the trial will complete the TCU ORC subscales that assess Adequacy of Resources (including Offices, Staffing, Training, Equipment, Internet, and Supervision) and Organizational Climate (including Mission, Cohesion, Autonomy, Communication, Stress, and Change). The TCU ORC has exhibited strong psychometric properties, and observed ORC subscale scores can be compared for interpretation against 25th percentile scores, 50th percentile scores, and 75th percentile scores reported from national data.¹⁴³

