To expand the accessibility and reach of CBT for anxious youth, a suite of self-paced, online, multimedia, CBT-based programs for youth anxiety was developed to run parallel to the therapist-led *Cool Kids* program. This online suite of programs covers identical content in a largely self-administered format. Similar to Therapist-Led *Cool Kids*, the *Cool Kids Online* suite of programs is comprised of separate developmentally tailored online programs, two of which were used in the present trial, depending on the age of the child: (1) “Cool Kids Online” for ages 7-12 years, and (2) “Chilled Out” for youth ages 13-18.^{54,105,106} These programs consist of 8 modules that are to be completed on a roughly weekly basis allowing for well-matched and time-equitable comparisons to the Therapist-Led CBT comparator. The online programs have already been used in numerous countries and are available in multiple languages, including Spanish. The programs include the same core CBT components as the Therapist-Led *Cool Kids* programs, feature interactive, engaging formats, and include video and audio clip examples of how to implement skills. In Cool Kids Online, caregivers take on the role of their child’s coach, helping them put their skills into practice, and learn helpful ways of responding to their child’s anxiety. In the Chilled Out adolescent online version, the teen takes primary responsibility for program completion, and there are features designed to specifically increase teen engagement—e.g., there are real teens featured in the videos, teens demonstrate skills for managing anxiety, and there is a “playlist” menu where teens can choose to re-visit content and cover skills at their own pace. The programs were originally developed in Australia. For both Cool Kids Online and Chilled Out, “Americanized” versions of the programs were used that include videos with diverse representation (e.g., American children, families, and experts; broader representation of individuals of color; removed Australian accents or vernacular).

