To foster supportive accountability and engagement,^{67,68} families in this condition receive brief phone check-in calls (i.e., < 15 minutes) from a therapist every other week. To ensure these brief calls do not drift into treatment sessions, therapists work from a conversation guideline to standardize calls (with space for flexibility as appropriate). Therapists should begin each check-in call with an explanation of the purpose of the call—i.e., to see how their use of the online modules is going, to find out whether the child/teen/caregiver has any questions, to support the family with the program, and to make a plan for continued practice. Therapists then check in briefly about each of the following components: (a) engagement with online program and activity completion (“Were you able to log into the online program? If not, what got in the way?”); (b)

identification of current difficulties/barriers, including technical or motivational challenges (“Did anything get in the way of completing activities or practice? Did you experience any difficulties as a parent with respect to your child/teen’s anxiety management?”); (c) brainstorming possible solutions to identified barriers (“Let’s see if we can problem-solve together and come up with some solutions to help you complete materials this week”); (d) review of anxiety and caregiver progress (“Has your/your child’s level of anxiety changed since beginning the program?); (e) technical questions about content (“Do you have any specific questions about the material that you learned in the modules you completed?”); (f) assignment/plan for next two weeks, providing encouragement and praise for even small successes; and (g) confirmation of the next call.

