Treatment fit and flexibility. As part of the *Session Summary Form* completed by the therapist after each treatment session (for Therapist-Led CBT cases) or check-in call session (for Guided Online CBT cases), therapists will indicate their level of agreement with the following statement on a scale from 0 (*not at all*) to 6 (*extensively*): "To what extent was the content covered this [session/check-in call] a fit to this child's clinical presentation and individual needs?" To assess needs for treatment flexibility, therapists will also indicate after each session their level of agreement with the following statement on a scale from 0 (*not at all*) to 6 (*extensively*): "How much did you need to tailor or adapt the content or structure of this session because of the child's clinical presentation and individual needs?" Moreover, as part of the *Session Summary Form*, therapists will select the reason(s) they may have covered content outside of the treatment protocol in the session they just held from a list of options (if relevant): (a) had to address a clinical emergency that made them concerned about immediate safety, (b) needed to

address a topic of the week that did not directly relate to the focus of the treatment protocol (e.g., family conflict, school trouble), (c) had to address a co-occurring/co-presenting issue other than child anxiety (e.g., ADHD, medical problem), (d) needed to engage in an alliance-building activity, (e) needed to address treatment resistance, (f) other (describe).

Treatment engagement and barriers. Therapists will complete weekly logs reporting whether study families on their caseloads attended their scheduled sessions or support calls and whether they completed the homework assigned in their previous session or support call. These data will be used to characterize *Treatment Attendance* and *Homework Engagement*. *Treatment Completion* is defined for Therapist-Led CBT as attending 10 treatment sessions, and for Guided Online CBT Care as attending 4 support calls. For Guided Online CBT families, administrative backend data will also be collected from the central server to further assess user/usage analytics.

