7.15.1.1 Therapist Contacts During the Treatment Phase for Guided Online CBT

Participants. Before the beginning of treatment in the guided online CBT arm, the following points of engagement must occur:

1. The therapist providing supportive accountability for the case must reach out to the patient over the phone or online to introduce themselves to boost patient engagement.
2. A technical orientation on the self-paced online program must take place with the participant. The technical orientation will be conducted using tools provided by the lead site. This orientation will go over how to navigate the program and who to contact with technical issues. This orientation can be conducted in-person, over the phone or via videoconference using Zoom software. The participant will always be

given the option to either attend the orientation in-person, on the phone, or via videoconferencing.

3. Participating families in this condition are given up to 20 weeks (i.e., the treatment phase) to complete their treatment program.
4. The therapist will work with the participant (and/or their family) to schedule check-in calls every 2 weeks. Throughout the duration of the program, these check-in calls will be held with the family or caregiver for children ages 7-12, and will be held with the child for children ages 13-18.
5. The participating family is guided to complete one self-administered module of the program each week. Families are encouraged to revisit and review completed modules as frequently as they wish.
6. The therapist will call the guardian and/or child every 2 weeks to check-in and provide supportive accountability. For each scheduled check-in/supportive accountability call, therapists should make at least 3 attempts to contact the family.
7. Therapists are to complete will complete a brief session log on REDCap after every check-in/supportive accountability call.

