7.15.1.2 Therapist Contacts During the Treatment Phase for Therapist-led CBT Participants

1. Participating families in this condition are given up to 20 weeks (i.e., the treatment phase) to complete their treatment program.
2. Each therapy session should be scheduled for 50-60 minutes. Therapists are advised to schedule families for roughly one therapy session per week.
3. Therapists can schedule multiple sessions a given week to help “catch up” if cancellations, missed appointments, holidays, or schedule breaks places them behind schedule.
4. Therapists are to complete will complete a brief session log on REDCap after after every treatment session.

*All clinics will work with their team to establish a workflow that is conducive to the procedures established above. This workflow will be shared with the lead site and any changes will be reported within a week of implementing the updated workflow.

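### Guided Online treatment completion counts four support calls and no modules, so it records support contact rather than receipt of treatment and is not comparable with the Therapist-Led rate

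*Combined protocol and SAP*

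**What the plan says.** Section 7.6.3 (Treatment engagement and barriers) states that completion "is defined for Therapist-Led CBT as attending 10 treatment sessions", and "for Guided Online CBT Care as attending 4 support calls". It adds that, for online families, "administrative backend data will also be collected from the central server to further assess user/usage analytics"; those data do not enter the definition.

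Section 7.2 places the online content in modules: "These programs consist of 8 modules that are to be completed on a roughly weekly basis". The therapist's part is "brief phone check-in calls (i.e., < 15 minutes) from a therapist every other week". The call follows a guide meant to stop it becoming a treatment session, and the guide has the therapist ask whether the family managed to log in at all. Section 7.15.1.1 repeats the schedule: "The therapist will call the guardian and/or child every 2 weeks to check-in and provide supportive accountability". In the other arm, Section 7.15.1.2 says: "Each therapy session should be scheduled for 50-60 minutes". Both arms have up to 20 weeks.

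Treatment completion is one of the engagement items listed in Section 6.2.2 under secondary and exploratory outcomes.

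**The concern.** The online treatment is the modules; the calls support their use. A completion measure that counts only calls can be met with none of the treatment received, and missed with all of it received. In the Therapist-Led arm the counted contacts are the ones in which content is delivered. The same word therefore covers two different quantities.

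Section 2.5 says attrition can be high in self-administered online care, so how much of the programme online families finish is something readers will want to know. The completion figure as defined cannot tell them. Any between-arm comparison of completion, which the Aim II objective on engagement and the Aim III models in Section 7.16.6 invite, would mix a difference in yardstick with a difference in engagement.

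**Working it through.** **Where the 4 comes from.** Eight modules at about one a week take 8 weeks. One call every 2 weeks gives 8 / 2 = 4 calls. The documents do not state this derivation, but it reproduces the threshold. Over the 20-week window there are 20 / 2 = 10 call slots, so the rule is also met by 4 of 10.

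**Classification under the rule as written.**
- 4 calls, 0 of 8 modules: complete.
- 3 calls, 8 of 8 modules: not complete.

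**Minimum therapist contact for a completer.** Guided Online: 4 × under 15 = under 60 minutes. Therapist-Led: 10 × 50 to 60 = 500 to 600 minutes.

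**Size of the lean when engagement is equal.** The documents give no expected completion rate, per-contact retention or attendance rate, so these inputs are assumptions shown over a range. Three meanings of equal engagement are plausible.

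(a) Equal weekly retention p: four calls span 8 weeks and ten sessions span 10, so compare p^8 with p^10.
(b) Equal retention p per planned contact: compare p^4 with p^10.

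| p | Guided Online, (a) p^8 | Guided Online, (b) p^4 | Therapist-Led, p^10 | Gap (a) | Gap (b) |
|---|---|---|---|---|---|
| 0.98 | 85.1% | 92.2% | 81.7% | 3.4 | 10.5 |
| 0.95 | 66.3% | 81.5% | 59.9% | 6.5 | 21.6 |
| 0.90 | 43.0% | 65.6% | 34.9% | 8.2 | 30.7 |
| 0.85 | 27.2% | 52.2% | 19.7% | 7.6 | 32.5 |

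(c) Equal probability q of attending each slot offered in 20 weeks: compare P(at least 4 of 10 biweekly calls) with P(at least 10 of 20 weekly sessions), both binomial.

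| q | Guided Online | Therapist-Led | Gap |
|---|---|---|---|
| 0.40 | 61.8% | 24.5% | 37.3 |
| 0.50 | 82.8% | 58.8% | 24.0 |
| 0.60 | 94.5% | 87.2% | 7.3 |
| 0.70 | 98.9% | 98.3% | 0.7 |

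Gaps are in percentage points, Guided Online minus Therapist-Led. None leans materially toward Therapist-Led.

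**How easily it could be cancelled.** Against 0.95 in Therapist-Led, the online advantage disappears if online retention falls to 0.95^(10/4) = 0.88 per call under (b), or 0.95^(10/8) = 0.94 per week under (a).

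**Chance of a nominally significant difference from the definition alone.** With 150 per arm and a two-sided 0.05 test (sidedness is an assumption), at p = 0.95 this is about 21% under (a) and about 99% under (b).

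**The case against.** The strongest defence is that both thresholds equal 100% of the therapist contacts planned at the intended pace: ten weekly sessions, and four biweekly calls for eight weekly modules. On that view the large gaps under (b) arise because a biweekly call and a weekly session are given the same dropout, which halves the weekly dropout rate online. With equal weekly dropout the gap is modest, and the four-call rule gives the same 66% as an eight-module rule at 5% dropout. This stands as an argument about size. It does not answer the classification problem, because that model assumes calls and modules move together and the definition does not require them to.

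It is also fair that the Therapist-Led definition counts sessions attended, not protocol sessions covered; Section 7.6.3 records coverage separately and allows for off-protocol content. Neither definition is a pure measure of content received, though attended sessions are where that arm's content is delivered. Therapists may also schedule extra sessions in a week to catch up (Section 7.15.1.2), which model (c) ignores.

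Two stronger readings are tempting and are not supported. A reader might infer that the trial will show better completion online. The documents give no attendance figures, and Section 2.5 warns of high online attrition, so the observed difference could favour either arm. A reader might also infer that four calls trigger the posttreatment assessment and so shift its timing by arm. Sections 7.1 and 7.15.2 tie that trigger to finishing the allocated programme without citing the 7.6.3 definition, and Section 8.3 describes reports on completed sessions or modules, which points away from calls. What remains is that the plan does not say which definition governs.

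**Conclusion.** The point holds as a defect in an outcome definition. As written, Guided Online completion measures support contact, misclassifies families in both directions with respect to treatment received, and cannot be set beside the Therapist-Led rate. That conclusion rests on the text alone.

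The lean toward Guided Online rests on assumed equal engagement, and its size depends on what is held equal; no single figure from the tables should be quoted as the bias.

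The stakes are limited. Completion is a listed secondary or exploratory item with no test of its own, the Aim II models in Section 7.16.5 predict anxiety severity, Aim III is exploratory, and the primary intention-to-treat analyses do not use the definition. Usage data are collected, so a content-based figure can be produced; the plan does not commit to one under the name of completion. The definition should be changed, but the trial's main conclusions do not depend on it.

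**What to change.** 1. Define Guided Online completion as 8 of 8 modules finished according to the server log.
2. Keep the four-call count as a separately reported support-attendance measure, so the prespecified figure stays visible.
3. Compare arms on the proportion of programme content received: distinct modules finished / 8 against distinct protocol sessions covered / 10. Counting each once avoids inflation from revisited modules or repeated sessions.
4. State that the midtreatment and posttreatment triggers in Sections 7.1, 7.15.2 and 8.3 use this same session/module definition.

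This changes outcome wording only and nothing offered to families. Section 8.5 already lists module completion time and content accessed among the server data, and the session form in Section 7.6.3 already records the protocol session numbers covered.

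The costs are that the online completion rate may look lower, and that a prespecified definition is being altered. Some text in Sections 7.2 and 7.6 is in the past tense, so data collection may be under way. If so, the change should be documented as an amendment made before between-arm data are examined.

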Adverse childhood experiences. The Center for Youth Wellness (CYW) *Adverse Childhood Experiences Questionnaire* (CYW ACE-Q)¹³¹ will be used to assess stressful life experiences that can impact child adjustment and development. From a list of 19 specific adversities, caregivers and youth ≥ 13 years will each report on the total number of challenging circumstances that participating children and adolescents have endured or encountered. This list includes 10 items from the original conceptualization of adverse childhood experiences (e.g., physical, emotion, and sexual abuse; physical and emotional neglect; household dysfunction; living with family members who misuse substances; living with family members with mental illness), as well as a broadened set of 9 additional experiences that can similarly cause prolonged stress that were not included in the original ACES conceptualization (e.g., death of a caregiver, exposure to neighborhood violence; immigration- or deportation-related separation from caregiver; identity-based discrimination; abuse or threats from a romantic partner). Two more additional items were also added to assess whether the child had directly experienced a natural disaster (e.g., earthquake, tornado, wildfire, hurricane) or a manmade disaster (e.g., terrorist attack, mass shooting, plane crash, industrial fire/explosion, bridge collapse). Respondents will review the list of items, tally the number of these experiences that the child has endured, and report that total number. Accordingly, the quantity of experienced ACES will be assessed, but information will not be collected for the research record that clarifies which specific ACES were experienced by the child. Per guidelines for the CYW ACE-Q, scores between 1 and 3 indicate "moderate exposure" to ACES and scores ≥ 4 are considered "high" and indicate "considerable exposure" to ACES.

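### The plan adds two disaster items to the 19-item ACE list and appears to record one total, yet quotes the CYW ACE-Q bands without limiting them to the 19 items.

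*Combined protocol and SAP*

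**What the plan says.** The relevant text is the adverse childhood experiences paragraph of section 7.6.4.

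- The instrument is the CYW ACE-Q. It begins "From a list of 19 specific adversities, caregivers and youth" aged 13 or over, who each report a total.
- The list is built from two parts: "This list includes 10 items from the original conceptualization of adverse childhood experiences" and "a broadened set of 9 additional experiences that can similarly cause prolonged stress".
- The study then extends it: "Two more additional items were also added to assess whether the child had directly experienced a natural disaster", plus a parallel item on manmade disaster.
- After that extension, respondents go through the list, "tally the number of these experiences that the child has endured, and report that total number".
- By design, "information will not be collected for the research record that clarifies which specific ACES were experienced by the child".
- The paragraph closes with the CYW cut-offs: 1 to 3 is moderate exposure, and 4 or more is high.

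Table 6, in the same section, gives two measure names for this domain, CYW ACE-Q and Expanded ACE-Q, and schedules it at all four assessments. Neither name is tied to a scoring rule anywhere. Section 7.16 does not mention the ACE score.

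**The concern.** The cut-offs are cited from the guidelines for the 19-item instrument. If the only recorded number counts 21 items, the bands are applied to a quantity they were not cited for. Because item answers are deliberately not kept, the two added items cannot be removed afterwards. This goes beyond a missing detail: followed as written, the procedure discards the information that the quoted cut-offs need, and no later data cleaning can restore it.

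What is at stake is the interpretation of one collected predictor. Section 6.3.2 gives adverse childhood events as an example of a factor neglected by earlier large trials, and section 4.2 says additional factors are assessed for further predictor and moderator tests. Any description or analysis of youth with high ACE exposure would rest on this score.

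**Working it through.** **Inputs from section 7.6.4.** Original items: 10. Broadened set: 9. Study-added disaster items: 2. Bands: 0; 1 to 3; 4 or more.

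**Item count.** 10 + 9 = 19, which reproduces the plan's figure. With the disaster items, 19 + 2 = 21.

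**What a single 21-item total T reveals.** The disaster items contribute 0, 1 or 2, so the 19-item score is T, T − 1 or T − 2, restricted to 0 to 19.

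| Total T | Possible 19-item scores | Possible bands | Band if applied to T |
|---|---|---|---|
| 0 | 0 | 0 | 0 |
| 1 | 0, 1 | 0 or 1–3 | 1–3 |
| 2 | 0, 1, 2 | 0 or 1–3 | 1–3 |
| 3 | 1, 2, 3 | 1–3 | 1–3 |
| 4 | 2, 3, 4 | 1–3 or ≥4 | ≥4 |
| 5 | 3, 4, 5 | 1–3 or ≥4 | ≥4 |
| ≥6 | all at least 4 | ≥4 | ≥4 |

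The exact 19-item score is known only at T = 0 and T = 21. The band is certain at 0, 3 and 6 or more, and ambiguous at 1, 2, 4 and 5. Since T is never below the 19-item score, banding T can only place a child too high.

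**Illustration of size (assumed inputs, none from the documents).** Let the 19-item score be Poisson with mean m from 1 to 3. Let a proportion p, from 5% to 50%, endorse the natural-disaster item and q = 2% the manmade item, all independent. A child is placed too high with a score of 0 or 3 and at least one disaster item, or with a score of 2 and both:

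share too high = [P(0) + P(3)] × [1 − (1 − p)(1 − q)] + P(2) × p × q

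- Largest case (m = 1, p = 0.50): (0.368 + 0.061) × 0.51 + 0.184 × 0.01 = 0.221, about 22%.
- Smallest case (m = 3, p = 0.05): (0.050 + 0.224) × 0.069 + 0.224 × 0.001 = 0.019, about 2%.

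Over the same grid, the share of children with T equal to 1, 2, 4 or 5, whose band cannot be confirmed, runs from 59% to 69%.

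**The case against.** The strongest reply is that a single tally is inferred. The paragraph first ties the reported total to the list of 19 and mentions the added items only afterwards. It never says outright that they enter the same count, and the two names in Table 6 would fit two scores. This stands in part: a second score is possible. But the instruction to tally comes after the additions and refers to one total, and nothing describes a second. If two tallies are in fact collected, the plan still has to define them and say which one is banded.

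It can also be said that the bands are only interpretive guidance, since section 7.16 specifies no ACE analysis, banded or otherwise. That is correct, and it limits the weight of the point. Section 7.16.4 would admit the score as a covariate if it differed between arms at baseline, but that route is conditional and serves adjustment only.

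A reader might infer more: because hurricane is among the natural-disaster examples and Miami is a site, the score would be inflated there and an ACE finding would partly be a site finding. The documents do not support this. Hurricane is one of four examples, and no disaster exposure is given by site. Site is already a covariate in every model (section 7.16.3) and a randomization stratum (section 7.5). No site-by-time or site-by-condition-by-time term is specified, so the main effect would not absorb every site difference, but that remains a conjecture without exposure figures.

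**Conclusion.** The point holds as a scoring defect in a secondary or exploratory predictor. On the natural reading of section 7.6.4, the recorded number is a 21-item count, the 19-item score is generally unrecoverable, and the quoted bands are not limited to the items they belong to. Any error from banding the total directly runs upward.

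It would be too strong to say that the bands are lost altogether, because they remain certain at 0, 3 and 6 or more. The ambiguous totals are, however, those next to the cut-offs. The 2% to 22% and 59% to 69% figures show a plausible scale only: they depend on the assumed score distribution, endorsement rates and independence. Randomization, the primary outcomes and the Aim I treatment comparison are not threatened.

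**What to change.** On the same form, record two numbers: a tally of the 19 CYW items and a separate tally, 0 to 2, of the disaster items. Define the first as the CYW ACE-Q score and the sum of both as the Expanded ACE-Q score, so that the names in Table 6 have a meaning. State that the 1-to-3 and 4-or-more bands apply only to the 19-item tally. If two tallies are already collected, only these definitions are needed.

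Where a record holds a single total, label it a 21-item count, analyse it as a count, and do not apply the CYW bands. Banding only the records where the band is certain would leave out those around the cut-offs.

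The cost is one extra REDCap field and a sentence or two in the plan. Single-total records stay unbanded. The privacy design is essentially kept, since the 19 items are still reported only as a count, although a disaster tally of 0 or 2 does reveal the answers to those two items. The sponsor should confirm that this is acceptable.
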